10.6.1.1 Relationship of AEs to Dose During the OLE Phase

The exposure-adjusted subject incidence of TEAEs (defined in [Section 6.3](#)) will be tabulated by the dose level of AMG 334 that the subject was receiving on the onset date for a specific TEAE. If a subject had his/her dose withheld or didn't receive IP at that dose level on the date of onset for a specific AE, the planned dose level will be assigned. The time of the first occurrence of the TEAE within each dose will determine the dose level. If a subject had multiple occurrences of the same AE both within a dose level, or at different dose levels, only the first occurrence within each dose level will be presented. Incomplete AE start dates will be imputed according to the algorithm defined in [Section 9.3.1](#).

Exposure-adjusted subject incidence of TEAE at a dose level = $(100 * \text{total number of subjects with the TEAE at the dose level}) / \text{total time (years) at risk for reporting the TEAE for subjects exposed at the dose level}$.

Total time (years) at risk for reporting a specific TEAE at a dose level = $\text{sum of all subjects' time (days) at risk for the TEAE at the dose level} / 365.25$.

For those who have experienced the TEAE, the time (days) at risk for reporting the TEAE at the respective dose level = time (days) at the respective dose level before the occurrence of the TEAE. The exposure-adjusted subject incidence of TEAEs will also be tabulated by the combined dose levels of AMG 334 by ignoring the dose level in which the TEAE occurred.

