Study Design: This is a multicenter, open-label study designed to assess the long-term safety and efficacy of AMG 334. Subjects who complete the 12-week double-blind treatment phase of the AMG 334 20120295 parent study and meet all AMG 334 20130255 eligibility criteria will be enrolled into the study. Enrollment should occur within 14 days of the week 12 visit of the AMG 334 20120295 parent study. Subjects who enroll in the AMG 334 20130255 study will end the AMG 334 20120295 study and will not participate in the parent study safety follow-up visit. Subjects may also elect to participate in a Novel Patient-reported Outcome Substudy in addition to a CHU substudy.

All subjects who have not yet enrolled in the study will receive open-label AMG 334 140 mg every month (QM) subcutaneous (SC) for 13 months. Subjects who are already enrolled in the 20130255 study will increase the open-label dose from 70 mg QM to 140 mg QM at the first available opportunity at either week 4, 8, 12, 16, 20, 24, or 28 visits. Subjects who have already

completed the week 28 visit will continue to receive 70 mg QM. Subjects will not have the option to decrease open-label AMG 334 from 140 mg QM to 70 mg QM. The 13-month open-label AMG 334 treatment phase will be followed by a 12-week safety follow-up visit (16 weeks after last dose of investigational product).

Sample Size: All subjects who completed the 12-week double-blind treatment phase of the AMG 334 20120295 parent study, meet the inclusion and exclusion criteria for the AMG 334 20130255 OLE study will be eligible to be enrolled. Up to 651 subjects may participate in the study.

Summary of Subject Eligibility Criteria: Adults with history of chronic migraine and who completed the 12-week double-blind treatment phase of the parent study. For a full list of eligibility criteria, please refer to [Section 4.1](#).

Amgen Investigational Product Dosage and Administration: Investigational product (IP) (ie, AMG 334 70 mg or 140 mg) will be dosed QM by SC injection. **For subjects participating in the CHU substudy, IP is AMG 334 140 mg in either a PFS or prefilled AI/Pen.**

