3.1 Study Design

This is a multicenter, open-label study designed to assess the long-term safety and efficacy of AMG 334. Subjects who complete the 12-week double-blind treatment phase (DBTP) of the AMG 334 20120295 parent study and meet all AMG 334 20130255 eligibility criteria will be enrolled into the study. Enrollment should occur within 14 days after the parent study's week 12 visit. **Subjects who enroll in the AMG 334 20130255 study will end the AMG 334 20120295 study and will not participate in the parent study safety follow-up visit.**

All subjects who have enrolled in the study under Protocol Amendment 3 or later, will receive open-label AMG 334 140 mg every month (QM) SC for 13 months. Subjects who enrolled in the 20130255 study, prior to Protocol Amendment 3, will increase the open-label dose from 70 mg QM to 140 mg QM at the first available opportunity at either week 4, 8, 12, 16, 20, 24, or 28 visits. Subjects who have already completed the week 28 visit will continue to receive 70 mg QM.

All subjects will receive open-label AMG 334 QM SC for 13 months followed by a 12-week safety follow up visit (16 weeks after the last dose of investigational product [IP]).

Investigational product AMG 334 70 mg or 140 mg will be dosed QM, SC.

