10.7 Pharmacokinetic or Pharmacokinetic/Pharmacodynamic Analysis

The pharmacokinetic concentration will be summarized with descriptive statistics by visit and treatment group using PK analyses set. Treatment group assignments will follow those specified for the efficacy analysis.

11. Changes From Protocol-specified Analyses

Since most subjects are likely to receive both 70 mg and 140 mg in this study, descriptive summaries on efficacy endpoints will be presented by randomized treatment group in the 20120295 parent study and first dose received in this study, and not by maximum dose as described in the protocol.

Bed days and missed work/school days due to migraine symptoms not summarized since they were not summarized in 20120295 parent study.

12. Literature Citations / References

Fairclough DL1, Cella DF. Functional Assessment of Cancer Therapy (FACT G): non-response to individual questions. Qual Life Res. 1996 Jun;5(3):321-9.

13. Prioritization of Analyses

Summary tables of safety and efficacy will be produced for the use of the annual report and to support publications, if warranted. Therefore, they might be prepared earlier than others.

14. Data Not Covered by This Plan

There are no plans to specifically analyze or summarize the following data points. However, a listing of these data may be presented and/or additional exploratory analyses may be performed should inspection of the data warrant.

- ECG data
- general comments
- population pharmacokinetics
- biomarker

15. Appendices

[figure not shown]

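### The by-dose adverse event rates in SAP 10.6.1.1 are not aligned on time on study, so with no dose effect they can still show a dose difference, in either direction

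*SAP*

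**What the plan says.** SAP 10.6.1.1, whose heading announces the relationship of AEs to dose, has TEAE incidence "tabulated by the dose level of AMG 334 that the subject was receiving on the onset date for a specific TEAE". The denominator is the "total time (years) at risk for reporting the TEAE for subjects exposed at the dose level". When an event recurs, "only the first occurrence within each dose level will be presented", so a switcher becomes at risk again on reaching 140 mg. SAP 10.6 gives the AE tables a 70 mg column, a 140 mg column and a total.

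On dosing, SAP 3.1 says that subjects enrolled before the amendment move up "at the first available opportunity at either week 4, 8, 12, 16, 20, 24, or 28 visits". The Protocol synopsis closes the other direction: "Subjects will not have the option to decrease open-label AMG 334 from 140 mg QM to 70 mg QM". Two groups do not switch. Later enrollees take 140 mg throughout, and for the others SAP 3.1 says "Subjects who have already completed the week 28 visit will continue to receive 70 mg QM". SAP Section 11 expects that "most subjects are likely to receive both 70 mg and 140 mg in this study". It gives this as the reason for summarising efficacy by parent-study arm and first extension dose. The by-dose AE tables get no comparable arrangement.

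**The concern.** Dividing by time at risk adjusts for how long each dose was taken. It does not adjust for when on study that time fell. In every switcher, 70 mg time is the first 4 to 28 weeks and 140 mg time is what follows. If AE reporting changes over the extension for reasons unrelated to dose, the change appears as a difference between the columns. None of the AE tables in SAP 10.6.1 and 10.6.1.1 is split by time on study, by entry dose or by dose sequence, although laboratory and vital sign summaries are by visit or over time. SAP 9.4 discusses bias without mentioning dose order.

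The section heading invites a comparison of the two columns, and AE incidence is the primary endpoint. Protocol 2.3 says the dose was raised to obtain more 6-month and one-year safety data at 140 mg, and SAP Section 8 foresees an interim safety analysis for a regulatory submission. What is at stake is how the columns are read; no test is planned.

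**Working it through.** The plan states no AE rate, subject mix or by-dose figure, so there is nothing of its own to reproduce. The check asks what the rule returns when the two doses have identical AE rates.

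**Inputs from the documents**
- Switch at week 4, 8, 12, 16, 20, 24 or 28, upward only (SAP 3.1; Protocol synopsis).
- Attribution by dose at onset, divided by time at that dose (SAP 10.6.1.1).
- Some subjects on 70 mg only and some on 140 mg only; numbers not given (SAP 3.1).

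**Assumptions**
- Switch weeks equally likely, 52 weeks of exposure, no dropout.
- Rate in weeks 0-12 equal to r times the later rate, the same at both doses.
- Mix 20% 70 mg only / 60% switchers / 20% 140 mg only, then varied.

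**Step 1: where a switcher's time falls.** For switch week w, averaged over the seven weeks:
- 70 mg, weeks 0-12: mean of min(w, 12) = 72/7 = 10.29 weeks
- 70 mg, later: mean of max(w - 12, 0) = 40/7 = 5.71 weeks
- 140 mg, weeks 0-12: mean of max(12 - w, 0) = 12/7 = 1.71 weeks
- 140 mg, later: mean of 52 - max(w, 12) = 240/7 = 34.29 weeks

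**Step 2: switchers alone.** The 70 mg rate is (72r + 40)/112 and the 140 mg rate is (12r + 240)/252, in units of the later rate. At r = 2 these are 1.643 and 1.048, ratio 1.57. At r = 1.5 and 3 the ratios are 1.29 and 2.09.

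**Step 3: everyone pooled, as the table does.** Each non-switcher adds 12 early and 40 later weeks to one column. Per subject enrolled:
- 70 mg: early 0.2 × 12 + 0.6 × 10.29 = 8.57; later 0.2 × 40 + 0.6 × 5.71 = 11.43; total 20.0
- 140 mg: early 0.2 × 12 + 0.6 × 1.71 = 3.43; later 0.2 × 40 + 0.6 × 34.29 = 28.57; total 32.0

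Weeks 0-12 thus supply 8.57/20 = 43% of 70 mg time but 3.43/32 = 11% of 140 mg time. The rates are (8.57r + 11.43)/20 and (3.43r + 28.57)/32.

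| r | 70 mg | 140 mg | 70:140 |
|---|---|---|---|
| 0.5 | 0.786 | 0.946 | 0.83 |
| 1 | 1.000 | 1.000 | 1.00 |
| 1.5 | 1.214 | 1.054 | 1.15 |
| 2 | 1.429 | 1.107 | 1.29 |
| 3 | 1.857 | 1.214 | 1.53 |

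**Step 4: other mixes at r = 2.** With 20% switchers (40/20/40), the rates are (2 × 6.86 + 17.14)/24 = 1.286 and (2 × 5.14 + 22.86)/28 = 1.184, ratio 1.09. With no switchers the ratio is 1.00.

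**Step 5: the SAP's first-event count.** A separate calculation applied the rule exactly, with risk restarting at the switch, follow-up to week 64 and a later rate of 5 per 100 subject-years. At r = 2 and the 20/60/20 mix it gave 6.95 at 70 mg against 5.42 at 140 mg, a 70:140 ratio of 1.28. At r = 3 it gave 8.92 against 5.84 (1.53), and at r = 0.5, 4.03 against 4.79 (0.84).

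**Step 6: align on time.** Within weeks 0-12 both columns have rate r, and afterwards both have rate 1, so the ratio is 1.00 in each interval. In the Step 5 setting, a Mantel-Haenszel rate ratio stratified by 4-week period was 1.000 in every scenario with switchers.

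**The case against.** The strongest reply is that this is a descriptive, single-arm estimation study (SAP Section 5) with no testing between safety groups (SAP 10.6), so no planned inference fails. That stands and limits the harm to interpretation.

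A reader might infer that the table will understate the risk of 140 mg. The documents do not support that: they give no AE rates over time. Several features argue for a modest early excess. Entrants have completed 12 weeks of the parent study without ending IP early, and those with an IP-related serious event there are excluded (Protocol 4.1). Some arrive already treated with AMG 334 (SAP 7.2). Parent-study events that continue without worsening are not counted (SAP 6.1.1). Moving to 140 mg also means two injections instead of one (Protocol 6.2.1.1), so reporting might partly restart at the switch. None of this can be quantified here.

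A reader might also carry the switchers-only ratios over to the planned table. They do not apply, because the table pools everyone, and non-switchers supply late 70 mg time and early 140 mg time.

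Nor is every safety display affected. The combined-dose column is untouched by ordering, though it compares no doses. Disposition by entry dose (SAP 10.2) and the timing of and reasons for withdrawal (SAP 9.4) will show departures on 70 mg. The narrower statement survives: no by-dose AE rate is aligned on time.

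**Conclusion.** The point holds in conditional form. By design the two columns draw on different parts of the study, and the rule can return a dose difference where none exists. Under the 20/60/20 mix the pooled 70:140 ratio is about 1.15, 1.29 or 1.53 for an early rate 1.5, 2 or 3 times the later one, 1.00 for a flat rate, and about 0.83 for an early rate half the later one. At a twofold early rate it falls to about 1.09 with 20% switchers, a share below the majority that SAP Section 11 expects.

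The flat-rate result assumes that subjects do not differ in their AE rates. With constant individual rates averaging 1 per year and gamma frailty variance 1, the first-event count gave 77.4 at 70 mg against 72.1 at 140 mg per 100 subject-years (77.4/72.1 = 1.07) with no time trend at all.

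Both size and direction rest on a mix and a time pattern that the documents do not state. The primary endpoint and the total column remain valid.

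**What to change.** Label: cheap improvement.

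1. Keep the SAP 10.6.1.1 table.
2. Add one table of TEAEs and SAEs by dose at onset within intervals since day 1 of the extension, for example 4-week or 12-week intervals. Optionally add a Mantel-Haenszel rate ratio stratified by 4-week interval.
3. State that the first occurrence is counted within each dose level and interval. If the existing rule ran on across intervals, switchers would restart at risk at 140 mg while subjects staying on 70 mg would not, which could bring back an imbalance when subjects differ in their AE rates.
4. Footnote the existing table: in switchers 70 mg time always precedes 140 mg time, so the crude columns are not a dose comparison.

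This needs no new data. The costs are sparse counts per interval and a dose comparison that remains non-randomised and tied to enrolment period. A comparison by entry dose over a common early window is a weaker choice. With 70 mg entrants censored at their first 140 mg dose, it discards all switchers' 140 mg time, rests on enrolment-period differences, and says little about long-term safety.

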9.2 Reporting of Adverse Events

9.2.1 Reporting Procedures for Adverse Events That do not Meet Serious Criteria

The investigator is responsible for ensuring that all adverse events observed by the investigator or reported by the subject that occur after first dose of investigational product through the end of study are reported using the applicable CRF (eg, Adverse Event Summary), including events that are reported to the Event Adjudication Committee for adjudication.

The investigator must assign the following adverse event attributes:

- Adverse event diagnosis or syndrome(s), if known (if not known, signs or symptoms),
- Dates of onset and resolution (if resolved),
- Severity,
- Assessment of relatedness to investigational product **and/or any study-mandated activity or procedure**, and
- Action taken.

The adverse event grading scale used will be the Common Terminology Criteria for Adverse Events (CTCAE). The grading scale used in this study is described in [Appendix A](#). The criteria for grade 4 in the CTCAE grading scale differs from the regulatory criteria for serious adverse events. It is left to the investigator's judgment to report these grade 4 abnormalities as serious adverse events.

If the severity of an adverse event changes from the date of onset to the date of resolution, record as a new event on the Adverse Event Summary CRF.

The investigator must assess whether the adverse event is possibly related to the investigational product. This relationship is indicated by a "yes" or "no" response to the question: "Is there a reasonable possibility that the event may have been caused by the investigational product?"

During the CHU, the investigator must assess whether the adverse event is possibly related to the IP and/or device. This relationship is indicated by a "yes" or "no" response to the question: Is there a reasonable possibility that the event may have been caused by the IP. The investigator must assess whether the adverse event is possibly related to the PFS or **prefilled** AI/pen used to administer IP. The relationship is indicated by a

“yes” or “no” response to the question: Is there a reasonable possibility that the event may have been caused by the device?

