6.1 Definition of Terms Included in Study Endpoints

6.1.1 Safety Endpoints

Serious Adverse Event (SAE)

SAEs determined by the flag indicating if the adverse event is serious on the Adverse Events (AE) eCRF page will include those that occur after signing of the informed consent and up to and including end of study.

Treatment-Emergent Adverse Event

Adverse Events (AEs) recorded on the Adverse Events eCRF page that occur on or after first dose of investigational product as determined by the flag indicating if the adverse event started prior to the first dose on the Adverse Events eCRF and up to and including 112 days after the end of investigational product (16 weeks after the last dose of IP) or end of study, whichever comes earlier.

An AE that started in parent study 20120295 is only considered treatment emergent in the OLE study 20130255 if there is a worsening of the event. If the event is ongoing with no changes in severity, then it will not be considered an AE in 20130255.

Treatment-Related Adverse Event

A treatment-related AE is defined as a treatment-emergent adverse event that is considered by investigators to have reasonable possibility that it may have been caused by IP as determined by the flag indicating if the event is caused by investigational product on the Adverse Events eCRF page.

Columbia-Suicide Severity Rating Scale (C-SSRS)

The C-SSRS is a clinician rating of suicidal behavior and ideation. The version "Since Last Visit" will be used for this study. The C-SSRS consists of a maximum of 20 items to evaluate suicidal behavior and suicidal ideation. Please refer to [Appendix B](#) for more details.

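### An adverse event that began on 70 mg and only eases after the step-up can be counted again at 140 mg, because no worsening rule applies at the dose boundary

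*SAP*

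**What the plan says.** Four rules act together.

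- **Recording (Protocol 9.2.1).** Sites are told: "If the severity of an adverse event changes from the date of onset to the date of resolution, record as a new event". The rule does not distinguish worsening from improvement. It stands in the section on events that do not meet serious criteria; Protocol 9.2.2, on serious events, does not repeat it.
- **Treatment-emergent status (SAP 6.1.1).** The definition is built on "Adverse Events (AEs) recorded on the Adverse Events eCRF page that occur on or after first dose of investigational product". A record opened for a grade change meets it. One filter follows: an event that started in the parent study "is only considered treatment emergent in the OLE study 20130255 if there is a worsening of the event".
- **Attribution and counting (SAP 10.6.1.1).** Incidence is "tabulated by the dose level of AMG 334 that the subject was receiving on the onset date for a specific TEAE". When the same event recurs within a level or at different levels, "only the first occurrence within each dose level will be presented". For a subject with the event, time at risk is the "time (days) at the respective dose level before the occurrence of the TEAE". A further tabulation is made "by the combined dose levels of AMG 334 by ignoring the dose level in which the TEAE occurred".
- **Dose path (SAP 3.1).** Subjects enrolled before the amendment "will increase the open-label dose from 70 mg QM to 140 mg QM at the first available opportunity", from week 4 to week 28. The protocol synopsis rules out going back to 70 mg. SAP 11 expects most subjects to receive both doses.

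**The concern.** A subject who has grade 2 constipation on 70 mg, easing to grade 1 shortly after the step-up, has two records. The second has an onset date on 140 mg. Read literally, the SAP counts the subject once under each dose, although nothing new happened on 140 mg and the event was improving.

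The SAP recognises this problem at the parent-to-extension boundary and handles it with the worsening filter. It has no counterpart at the 70-to-140 mg boundary inside the extension. Because dose only rises, re-logged events of this kind can enter only the 140 mg column. Protocol 2.3 gives additional 6-month and one-year safety data as the reason for raising the open-label dose to 140 mg. A persistent side effect of the lower dose could then read as an effect of the higher one.

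**Working it through.** The documents give no adverse event rate, no count of events ongoing at step-up and no share that changes grade, so there is no planned figure to reproduce. The check is one worked subject, then an illustration with assumed inputs.

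**One subject (assumed dates).** Step-up on day 85; grade 2 event starts on day 70; it eases to grade 1 on day 90 and is re-logged.

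- 70 mg: 1 event, 70 - 1 = 69 days at risk.
- 140 mg as written: 1 event, 90 - 85 = 5 days at risk.
- 140 mg without the re-log: 0 events. Follow-up to day 449 (week 48 dose on day 337, plus 112 days) gives 449 - 85 = 364 days.

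**Switchers as a group.** Assumptions: onset rate h, constant and equal on both doses; step-up at week 16, so 112 days on 70 mg; 140 mg follow-up T = 336/365.25 = 0.920 years; re-log t = 28/365.25 = 0.077 years after step-up; 30-50% of 70 mg events ongoing at step-up; 30-50% of those change grade.

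1. Share of switchers with any onset on 70 mg: q = 1 - exp(-h x 112/365.25). For h = 0.05 per year, q = 1.52%; for h = 0.02, q = 0.61%.
2. Share with a re-logged event: c = q x (ongoing share) x (grade-change share). For h = 0.05, the low case is 1.52% x 0.30 x 0.30 = 0.137% and the high case is 1.52% x 0.50 x 0.50 = 0.380%.
3. Tabulated rate per 100 subject-years = 100 x [(1 - c)p + c] / [(1 - c)p/h + ct], with p = 1 - exp(-hT). For h = 0.05, p = 0.04495 and p/h = 0.89908.
   - Low: 100 x 0.04626 / 0.89796 = 5.15.
   - High: 100 x 0.04859 / 0.89595 = 5.42.
4. If half of the grade changes are worsening, only half of c is spurious. Halving c gives 5.08 and 5.21.

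| Assumed rate | All re-logs counted | Spurious half only |
|---|---|---|
| 5 per 100 subject-years | 5.15-5.42 | 5.08-5.21 |
| 2 per 100 subject-years | 2.06-2.17 | 2.03-2.08 |

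**Front-loaded onset.** Keep h = 0.05 on 140 mg but suppose 3% of switchers, not 1.52%, had an onset on 70 mg. Then c = 0.27% to 0.75%, and the same formula gives 5.30 to 5.84.

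**Dilution.** Add an equal number of subjects on 140 mg from day 1 (assumed), followed for 448 days = 1.227 years. Each contributes 1 - exp(-0.05 x 1.227) = 0.0595 events and 1.190 years. The pooled rate is 100 x (0.04626 + 0.0595)/(0.89796 + 1.190) = 5.07 in the low case and 100 x (0.04859 + 0.0595)/(0.89595 + 1.190) = 5.18 in the high case.

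**The opposite effect.** A 70 mg event that continues unchanged has no record with onset on 140 mg, so the subject adds 140 mg time with no event. Compare with a stricter rate that takes subjects with an ongoing event out of the risk set. If a share g of ongoing events changes grade and the rest continue unchanged to the end, these subjects raise the 140 mg rate only if g exceeds hT/(1 + hT - ht):

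- h = 0.05: 0.0460/(1 + 0.0460 - 0.0038) = 0.044.
- h = 1.0 (a very common term, or the any-event row): 0.920/(1 + 0.920 - 0.077) = 0.50.

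**The case against.** The strongest reply has four parts.

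**Wording.** SAP 10.6.1.1 speaks of an occurrence of the same event, not of a record, so a downgraded continuation need not be a new occurrence, and programmers may link records. Neither document says so. The protocol calls the re-log a new event and the SAP defines treatment-emergent events from the eCRF. The point is therefore that the text permits the double count, not that it will certainly happen. The recording rule also sits in the non-serious section, so the point is limited to non-serious events.

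**Size.** A reader might infer that several percent of switchers carry an event across and that the 140 mg rate could double. At a constant rate of 5 per 100 subject-years only 1.52% of switchers would have had any onset by week 16, and at 2 only 0.61%. Shares of 2-5% would need a higher or front-loaded 70 mg rate, which the documents do not give. This stands.

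**Direction.** A reader might infer that the 140 mg rate is always inflated. Relative to not counting the re-log, it can only rise. Against a rate that removes ongoing cases from risk, the net direction is not assured for very common terms or the any-event row. This stands too. Events that truly worsen on 140 mg are also legitimate 140 mg events.

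**Consequence.** A reader might infer that the primary endpoint itself is compromised. It is subject incidence of adverse events with no dose contrast. SAP 10.6 adds a total group, and in the combined tabulation a re-log adds no count. SAP 5 and 10.6 plan no testing, and the dose columns are not randomised. This limits the consequence to the by-dose columns, but those are the columns meant to show how events relate to dose.

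**Conclusion.** The gap is real and narrower than it first appears. As written, a non-serious event that began on 70 mg and only eased after the step-up can count again at 140 mg and shorten that subject's 140 mg time at risk. This can bias the 140 mg by-dose rates upward for persistent terms.

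Under equal constant rates and the stated assumptions, a rate of 5 per 100 subject-years becomes about 5.2-5.4 among switchers, with about half the excess spurious if half the grade changes are worsening. The shift is larger if onset is front-loaded and smaller once subjects on 140 mg from day 1 are pooled in. The true size cannot be derived from the documents. They do not support a claim of large or certain inflation, or of any effect on the combined column.

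**What to change.** In SAP 10.6.1.1:

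1. Chain contiguous records of the same preferred term within a subject into one episode, with a stated rule for how close an end date and the next start date must be.
2. Apply the worsening principle of SAP 6.1.1 at the 70-to-140 mg boundary. Count an event at 140 mg only if it is a new episode, or if its CTCAE grade rises above the grade held when the first 140 mg dose was given.
3. State how a term ongoing at step-up enters 140 mg time at risk, for example by starting new-onset risk time for that term when the event resolves. Dropping the re-log while crediting full event-free 140 mg time would enlarge the opposite bias shown above.

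The cost is a few sentences of SAP text, a date-linking rule and one programming step. No new data are needed. The small downside is that the linking rule involves a judgement about gaps between dates, so it should be fixed before the by-dose tables are run.
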